1.2 RATIONALE FOR CURRENT STUDY

This research proposal is a bolt-on mechanistic study, affiliated to an NIHR HTA/Kidney Research UK-funded UK multicentre randomised controlled trial to assess the safety and efficacy of rituximab + standard of care (SOCR) compared with SOC in treating acute antibody-mediated rejection (AAMR) in kidney transplantation (TAR:GET-1)(Transplant Antibody Mediated Rejection: Guiding Effective Treatments; ISRCTN pending, EudraCT ref 2018-002882-20). This phase 3, 2-arm, open-label randomised controlled trial will enrol patients with biopsy-proven AAMR and randomise them to SOCR versus SOC (85 patients in each arm). The trial is scheduled to start in Spring 2019, and patients will be recruited over 40 months, then followed up for 4 years post treatment (follow up complete late 2026). The primary objective is efficacy, with graft survival at 4 years the primary end point.

Analysis of B cell, antibody and biopsy characteristics of patients enrolled in TAR:GET-1 will address several questions:

1) Which patients with a diagnosis of AMR require additional immunosuppression?

It is recognised that AAMR is a heterogeneous disease, and there is evidence that severity of the individual diagnostic features at presentation (HLA antibody strength, biopsy Banff scores) is associated with outcome. Novel parameters not yet used in routine diagnosis also hold promise in increasing diagnostic accuracy and directing treatment; these include complement-activating ability of DSA (Viglietti 2017, Sicard 2015, Bouquegneau 2018), the AAMR-related gene expression signature level (Loupy 2014, Halloran 2016), and B cell characteristics (genomic, transcriptional and functional). The data from past investigations is contradictory, most often derived from retrospective observational studies without uniform

Mechanistic Evaluation of Treatments for Acute Antibody-Mediated Rejection of the Kidney Transplant (M.O.T. AMR) – Version 1.4 27/05/2020

follow-up and treatment, and often lacks robust multivariate analyses. There is insufficiently robust evidence to promote risk stratification and selection of patients for additional treatment.

2) How can we tell if treatment is working?

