Serial measurements of the strength of DSA and severity of biopsy features have been used to describe the natural history of AAMR and to determine response to treatments, including rituximab. There is evidence in the literature that treatment of AAMR may reduce antibody strength and/or affect complement-activating ability (Cioni 2018, Viglietti 2018b, Bailly 2018, Lefaucheur 2018) and may have a positive effect on biopsy scores (Viglietti 2018a, Sautenet 2016, Eskandary 2018, Choi 2017) or transcript levels (Eskandary 2018, Lefaucheur 2018). Immunosuppression can induce changes in B cell gene expression and functional profile (Banham 2018). However, the evidence is inconclusive and in places contradictory, and has not been validated in the context of randomised controlled trials. Therefore, serial measurements are not yet used to guide treatment decisions.

3) The need for surrogate endpoints for clinical trials in AMR

Given that the end point for trials in AAMR (graft loss) is remote, development of surrogate end points for AAMR trials is a priority (Velidedeoglu 2018). Longitudinal assessment of biomarkers in patients with AAMR has been shown to assist in outcome prediction, but here again data is limited (Viglietti 2018a). This project provides an opportunity to investigate potential surrogate markers of outcome.

This MOT-AMR research proposal has 2 hypotheses:

Hypothesis 1: AMR is a heterogeneous disease, with outcome and response to treatment accurately predicted by mechanistic biomarkers (B cell, DSA and biopsy features) at baseline, including more recently characterised complement-activating ability of DSA and AAMR gene expression biopsy signature.

Hypothesis 2: Although the clinical endpoint of TAR:GET-1 is graft loss, effective AAMR therapy will be reflected in changes in mechanistic features in serum and in biopsies. In the case of treatment with rituximab, this is achieved through favourable changes in B cell characteristics.

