3. STUDY DESIGN

Patient Cohort

This is a prospective cohort study using samples from all patients enrolled in the TAR:GET-1 (170 patients, 85 in each arm). The TAR:GET-1 trial will recruit patients starting in June 2019, over a period of 4 years, and patient will be followed up with further biological samples taken over a further period of 4 years. This will need to be analysed for which we estimate a further 2 years. The total duration of the study is therefore 10 years starting June 2019.

We aim to collect all samples from each patient to maximise the information obtained, whilst incurring negligible extra risk to the study participants.

Some of the samples are already obtained as part of the TAR:GET-1 protocol and we will use left over material to carry out analyses.

Some of the samples are not routinely obtained for TAR:GET-1 enrolment, but the TAR:GET-1 protocol and consent process covers their (optional) collection.

The only extra samples that requires a new consent process as part of M.O.T.-AMR is an optional post-treatment protocol biopsy.

The study aim is to be a comprehensive assessment of antibody-mediated rejection biomarkers pre- and post-treatment, but has below been artificially divided into Parts 1 and 2, Part 1 being funded by Imperial BRC, Cambridge BRC and NIHR EME (funding secured) whereas applications for funding for Part 2 are in process. A funding approval letter will be provided to the Sponsor and REC committee prior to commencing any element of part 2 of the study, and will specify which further specific elements of the study have received funding approval.

Samples taken as part of TAR:GET-1:

Patients enrolled in TAR:GET-1 will have a number of samples taken, and consent for enrolment in TAR:GET-1 includes agreement to the use of extra material left after diagnosis for research. We will therefore be able to access in 100% of patients enrolled in TAR:GET-1:

- Enrolment biopsy material
- Serum samples taken for DSA measurements
- Post-treatment indication biopsies taken as part of routine clinical care.

TAR:GET-1 is already assessing DSA MFI, DSA target and B lymphocyte numbers at baseline and 3 months post-treatment. In addition to these, M.O.T.-AMR will analyse in left over material from these routine samples:

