Specifically for M.O.T-AMR, patients enrolled in TAR:GET-1 will be offered an optional protocol biopsy at 6 months post-treatment. This additional sample is optional and M.O.T.-AMR is not dependent on it being obtained. This protocol biopsy will be carried out in the local centre, by the local clinical team. A post-treatment protocol biopsy is a biopsy taken in a patient with stable transplant function and no indication for a biopsy to be taken. The literature suggests that this a useful tool for monitoring response to treatment (Viglietti 2018a), but strong evidence from randomised controlled trials such as TAR:GET-1 is lacking for its routine introduction into clinical care and therefore, in most centres a post-treatment protocol biopsy is not offered to patients. The protocol biopsy will be collected for research and costed as research. Biopsy results on these protocol biopsies will be made available to the clinicians if any unexpected findings that need to be acted upon for patient benefit are noted. We will carry out the same histological and transcriptional investigations on these biopsies as for the enrolment and indication biopsies. A conservative estimate of protocol biopsy acceptance is 50%, based on our local experience (85 samples), and this is the number of samples we aim to achieve.

Funding:

Part 2: Funding for taking these biopsies is covered by NIHR EME 129029. Shipping and analysis will be partly covered by Imperial BRC.

This table illustrates how visits and samples in TAR:GET-1 will be used for investigations in M.O.T.-AMR. The additional samples needed for M.O.T.-AMR are in italic.

TAR:GET-1 trial visits	Baseline	Unscheduled	Visit 3 (month 3)	Visit 4 (month 6)	Visit 5 (month 12)
Biopsy histology and gene expression analysis	Use leftover sample	Indication biopsy for graft dysfunction: Use leftover samples		Optional protocol biopsy	
Serum DSA characteristics and BAFF	Use leftover sample		Use leftover sample		Use leftover sample
B cell characteristics and Peripheral blood transcriptomics	2 extra blood tubes		2 extra blood tubes	2 extra blood tubes	2 extra blood tubes

Sample storage:

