7. STATISTICS AND DATA ANALYSIS

The patient cohort size is dictated by TAR:GET-1: 170 patients, 85 in each arm. Under plausible modelling assumptions, for any biomarker that is on the mechanistic pathway between treatment and primary outcome, the power of the main study (90%) will be matched or exceeded when comparing the mean biomarker values between treatment groups. The mediation analysis will estimate for each biomarker the influence on allograft survival rate per unit change in biomarker, above and beyond, the direct effect of treatment. This will decompose the overall, marginal, treatment effect into a proportion attributable to a mechanism via the biomarker, and the complement attributable to direct effects, or other mechanisms. A similar multivariable analysis will proceed to estimate the mediation effects of multiple biomarkers acting in parallel, as an exploratory analysis using variable selection methods to control for over-fitting.

Data from this research project will be merged and linked with data from the TAR:GET-1 clinical trial by the statistician team.

Descriptive data

Mechanistic Evaluation of Treatments for Acute Antibody-Mediated Rejection of the Kidney Transplant (M.O.T. AMR) – Version 1.4 27/05/2020

This will include description of all the biological characteristics analysed in 2 populations (rituximab + SOC and SOC) at baseline and at all follow-up time points. Summary statistics (mean, median, SD, range for continuous variables, and frequency tables for categorical variables) will be reported broken down by treatment, with exploratory figures (box-and-whisker plots for continuous, and stacked bar-charts for categorical).

Outcome analysis

Appropriate measures of differences between treatment groups will be estimated with point estimates, 95% confidence intervals, and p-values. Depending on the type of variable (continuous, categorical, time-to-event), regression techniques (linear, logistic, cox) and transformation of the endpoints will be considered.

Differences in characteristics comparing pre- to post-treatment samples at sequential time points will be analysed comparing the 2 groups of patients (SOCR versus SOC) using mixed effect models repeat measurement techniques.

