Mediation analysis, a special case of regression analysis, will be used to document that the treatment effects a change in the biomarker. We will use mediation analysis models to decompose total effect of treatment effect on graft loss into an indirect effect, which measures how much of the effect acts through the intermediate variable(s), and a residual direct effect. All the mediation analyses will be based on the Intention-to-Treat principle. We will fit the same form of outcome models as for the efficacy analyses, including the mediator as a covariate. We will use the mediation package within R which was developed specifically to make valid causal inference in explanatory analyses of the mechanisms of treatment-induced change in clinical outcomes in randomised clinical trials. All estimates of treatment differences will be summarised using effect size estimates and 95% confidence intervals (Dunn 2013). Collaborator for mediation analysis: [name], Professor of Statistical Methods for Medicine, UCL

Data and all appropriate documentation will be stored for a minimum of 10 years after the completion of the study, including the follow-up period.

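### The mediation outcome model is worded as the efficacy form plus the mediator, with no baseline marker value named; followed as worded, the indirect effect can be biased in either direction

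*Protocol*

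**What the plan says.** Protocol section 7 (repeated in the Study Summary) specifies the mediation outcome model in one sentence: "We will fit the same form of outcome models as for the efficacy analyses, including the mediator as a covariate". It then names an R package, described as "developed specifically to make valid causal inference in explanatory analyses of the mechanisms of treatment-induced change in clinical outcomes in randomised clinical trials". No baseline marker value, and no other predictor of both marker and graft loss, is listed for this model. The efficacy models belong to TAR:GET-1 and their covariates are not given here.

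Pre-treatment values do appear in section 7, in the mixed model that compares markers before and after treatment. That is a separate analysis with the marker as the response, not the graft-loss model.

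On the link between baseline and outcome, section 1.2 says that "severity of the individual diagnostic features at presentation (HLA antibody strength, biopsy Banff scores) is associated with outcome", and Hypothesis 1 has "outcome and response to treatment accurately predicted by mechanistic biomarkers (B cell, DSA and biopsy features) at baseline". The same section also calls past data contradictory.

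The mediator's definition is not settled. Section 2 and Hypothesis 2 refer to changes in the markers. Section 7 expresses the effect per unit of change in the biomarker, which can mean a one-unit difference in level or a change from baseline.

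**The concern.** The decomposition of the treatment effect is the secondary objective, and section 1.2 looks to the study for possible surrogate markers. Both rest on the coefficient that links the marker to graft loss. That coefficient is observational even inside a randomised trial, because patients are randomised to treatment and not to their later marker value. A baseline value that predicts both the later marker and graft loss confounds it. An efficacy model has no need of such a covariate, so carrying its form over and adding only the mediator leaves the confounding in place. Choosing a mediation package does not supply the missing covariate.

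At stake is a marker being credited with benefit that it does not carry, or denied benefit that it does.

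**Working it through.** **What the documents supply.** 170 patients, 85 per arm, and graft loss at 4 years. They give no graft-loss rate, hazard ratio, marker shift, correlation or baseline effect. The only related figure is 90% power for comparing marker means, which cannot be reproduced because no significance level, difference or SD is stated. At an assumed two-sided 5%, 85 per arm has 90% power for (1.960 + 1.282) × √(2/85) = 0.497 SD, so a shift of 0.5 SD is a reasonable illustration. Everything below is assumed.

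**Set-up.** Baseline marker M0 and follow-up marker M1 have unit variance within arm and correlation r. Treatment shifts M1 by d. On the log-hazard (or log-odds) scale, M1 has effect b, M0 has effect g by another route, and treatment has direct effect c. The true indirect effect is d × b. The formulas are linear approximations.

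1. *Mediator is M1, baseline omitted.* The coefficient becomes b + r × g, so the indirect effect is d(b + r × g) and the error is d × r × g. It is zero when g = 0.
2. *Mediator is M1 − M0, baseline omitted.* The variance of the change is 2(1 − r). Its covariance with M1 is 1 − r and with M0 is −(1 − r). The coefficient is therefore (b − g)/2 at any r. With g = 0 it is b/2, half the true value.
3. *Baseline in both models.* The coefficient is b and the arm effect is d under either definition, so d × b is recovered.

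**Inert marker (b = 0).** d = −0.5, hazard ratio 0.6 (ln 0.6 = −0.511), 40% loss on standard of care. The follow-up-value formula is 0.5 × r × g / 0.511; at g = 0.4 and r = 0.6 it gives 0.12/0.511 = 23%. The Cox simulation agrees (share credited to the marker; truth 0%):

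| g per SD | r = 0.4 | r = 0.6 | r = 0.8 |
|---|---|---|---|
| 0 | 0.5% | -0.3% | 0.3% |
| 0.2 | 7.6% | 11.5% | 16.4% |
| 0.4 | 15.0% | 23.9% | 30.7% |
| 0.7 | 28.7% | 41.9% | 55.0% |

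With baseline added, the share lies between -1.1% and +0.9%. For the change score at g = 0.4, the coefficient is −0.2, the indirect effect is −0.5 × −0.2 = +0.10, and the share is 0.10/(−0.511), about -20%.

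**Real mediator.** d = −0.5, b = 0.6, c = −0.3, logistic outcome. The true share is 0.30/0.60 = 0.50. Simulated shares over r = 0.3 to 0.7:

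| g | Follow-up value, no baseline | Change score, no baseline | Baseline in both models |
|---|---|---|---|
| 0 | 0.49–0.50 | 0.24–0.25 | 0.49–0.50 |
| 0.4 | 0.60–0.73 | 0.08 | 0.49–0.50 |
| 0.8 | 0.70–0.97 | -0.08 to -0.09 | 0.50 |

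The formulas match these. For example, at g = 0.4 and r = 0.7 the follow-up share is 0.5 × (0.6 + 0.28)/0.6 = 0.73, and the change-score share is 0.5 × 0.1/0.6 = 0.08.

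**At the trial's size.** With 170 patients, 40% loss on standard of care, an inert marker and the follow-up value as mediator, a 95% interval wrongly excludes zero in 7.2/12.2/19.7% of trials at g = 0.2 (r = 0.4/0.6/0.8), against 5.4/3.9/4.6% with baseline added. At g = 0.4 the figures are 18.2/33.5/56.7% against 4.6/6.1/5.6%.

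**The case against.** The strongest objection is that this is silence and not error. The phrase about the same form of model most naturally means model type, and adding the mediator does not say that nothing else enters. A covariate list is often left to a statistical analysis plan, and TAR:GET-1 may already carry baseline marker values. Much of this stands. A reader might infer that the protocol excludes baseline adjustment; it does not. What remains is that the protocol does more than defer: it states how the model is built, ties it to a claim of valid causal inference, and leaves out a covariate whose relevance it argues for itself.

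A second objection concerns direction and size. A reader might infer that leaving out baseline always inflates the marker's share, by a known amount. The documents do not support that. The mediator is not fixed as a level or a change, and the two definitions give errors of opposite sign in the cases above. Over-crediting on the first definition also supposes that baseline and follow-up values act on graft loss in the same direction. This objection stands in full.

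Third, section 1.2 supports an association between baseline and outcome, which would also hold if baseline acted wholly through the later marker. For a follow-up-value mediator there would then be no bias. That is correct, but it does not rescue a change-score mediator, where a true indirect effect is halved even when g = 0.

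Fourth, adjustment has a price. With 20% loss and g = 0.2, the root mean squared error of the indirect log hazard ratio is 0.113–0.162 with baseline against 0.110–0.128 without. The gain there is in bias and false attribution, not in overall error.

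**Conclusion.** The point holds conditionally. If the mediation model is fitted as worded and the TAR:GET-1 efficacy model does not already contain the baseline marker, the indirect effect can be biased. With the follow-up value as mediator, this needs baseline to be correlated with follow-up and to affect graft loss by another route; the usual result is over-crediting. With change from baseline as mediator, the error can go the other way and does not need that route.

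The size cannot be settled from the documents. Under the assumptions shown, the share credited to an inert marker runs from about 0% to 55% on the follow-up definition and is about -20% on the change definition at a baseline log hazard ratio of 0.4.

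A reader might also infer that the trial's main results are in doubt. They are not: the total treatment effect and the primary comparison of markers between arms rest on randomisation and are unaffected. This is a cheap improvement to a secondary analysis.

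**What to change.** In section 7 and the Study Summary, state that the baseline value of the same marker, where collected, enters both the mediator model and the graft-loss model, whether the mediator is the follow-up value or the change from baseline. Add a sensitivity analysis for unmeasured mediator-outcome confounding, since baseline adjustment does not remove other shared causes.

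The cost is wording and one covariate per single-marker model, with no new samples. Section 3 says that "TAR:GET-1 is already assessing DSA MFI, DSA target and B lymphocyte numbers at baseline and 3 months post-treatment". Of enrolment biopsy material and DSA serum it says "We will therefore be able to access in 100% of patients enrolled in TAR:GET-1". PAXgene samples are expected in about 90% of patients and lithium heparin tubes in about 50%, subject to funding, so adjustment there is limited to patients with a baseline value.

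Some precision is lost. With 170 patients, 40% loss on standard of care and baseline not prognostic, the SD of the indirect log hazard ratio goes from 0.072/0.074/0.072 to 0.078/0.092/0.126 at r = 0.4/0.6/0.8. At a baseline log hazard ratio of 0.4 the trade is favourable: root mean squared error falls from 0.111/0.143/0.185 to 0.076/0.090/0.121. Both comparisons are for the follow-up value as mediator. With few graft losses and a weak baseline effect, the error can rise slightly, as noted above.

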8. REGULATORY ISSUES

8.1 ETHICS APPROVAL

The Chief Investigator has obtained approval from the Health Research Authority (HRA) and Research Ethics Committee. The study must also receive confirmation of capacity and capability from each participating NHS Trust before accepting participants into the study. The study will be conducted in accordance with the recommendations for physicians involved in research on human subjects adopted by the 18th World Medical Assembly, Helsinki 1964 and later revisions.

8.2 CONSENT

As part of the consent procedure for enrolment in TAR:GET-1 patients will:

- Consent for use of left over material from samples taken as part of TAR:GET-1 to be used for research
- Consent to be offered optional extra tubes of blood for research during the scheduled blood drawing events of TAR:GET-1

Mechanistic Evaluation of Treatments for Acute Antibody-Mediated Rejection of the Kidney Transplant (M.O.T. AMR) – Version 1.4 27/05/2020

We will separately obtain consent for use of TAR:GET-1 samples for this specific project (M.O.T.-AMR), and for an optional post-treatment protocol biopsy at 6 months after initiation of treatment.

The ICF and process for obtaining informed consent must comply with the applicable national and international laws, rules, and regulations. The ICF will document the study-specific information the Investigator or his/her designee provides to the subject and the subject's agreement to participate in the study and to comply with the instructions of the Investigator and study staff. The Investigator/designee will fully explain, in terms understandable to the subject, the nature of the study, along with the aims, methods, anticipated benefits, potential risks, and any discomfort that participation in the study may entail. The ICF must be signed and dated by the subject before the subject participates in any study-related activities. The original and any amended signed and dated ICFs must be retained in the subject's file at the study site, and a copy must be given to the subject at the time that it is signed by the subject. The Investigator must also maintain a log of all informed consents obtained.

Consent to enter the study must be sought from each participant only after a full explanation has been given, an information leaflet offered and time allowed for consideration. Signed participant consent should be obtained. The right of the participant to refuse to participate without giving reasons must be respected. After the participant has entered the study the clinician remains free to give alternative treatment to that specified in the protocol at any stage if he/she feels it is in the participant's best interest, but the reasons for doing so should be recorded. In these cases the participants remain within the study for the purposes of follow-up and data analysis. All participants are free to withdraw at any time from the protocol treatment without giving reasons and without prejudicing further treatment.

